5.2. Determination of Sample Size

For the Phase 1b dose escalation, a 3+3+3 design will be used to assess the safety of galunisertib in combination with nivolumab 3 mg/kg. Between 3 and 12 additional patients may be enrolled in a cohort to achieve the minimum of 3 evaluable patients if dropouts or dose interruptions or reductions occur that result in a patient being nonevaluable for DLTs.

Although the primary objective remains safety of the combination for the Phase 2 cohort expansion part, the sample size appears to be adequate to evaluate preliminary antitumour activity of the combination.

When the 25th patient from each cohort has completed at least 3 cycles, an interim analysis will be conducted. Two-stage design criteria (Simon 1989) will be used to evaluate whether additional patients for that cohort will be enrolled. The null hypothesis that the null response

rate is 20% will be tested against a 1-sided alternative. If there are 4 or fewer responses in the initial 25 patients who have been enrolled and either discontinued from their allocated treatment or completed at least 3 cycles, no additional patients will be enrolled. If there are \geq 9 responses, then no additional patients will be enrolled into this cohort in Phase 2. If there are 5 to 8 responses, then approximately 16 additional patients may be accrued for a total of approximately 41 patients for that cohort.

5.3. Method of Assignment to Treatment

This study is open-label for Phase 1b and Phase 2. Before each patient's enrolment into the study, an eligibility check must be conducted between the investigational site and the Lilly clinical research personnel to confirm that each patient meets all enrolment criteria. Upon confirmation of eligibility, the sponsor will confirm the dose and identification number assignment and cohort for each patient. No dose escalations (that is, to the next cohort) can occur without prior discussion and agreement between the investigator and the responsible Eli Lilly and Company (Lilly) CRP or clinical research scientist (CRS); the decision will be documented in writing. All patients must begin study treatment within 7 days of enrolment by interactive web-response system (IWRS).

For Phase 1b, if investigators have eligible patients who have consented concurrently, more than 3 patients (Cohorts 1 and 2) or 4 patients (Cohorts 3 or 4) may be entered at a particular dose level provided that accrual has not ceased due to excessive toxicity. This enrolment procedure is allowed because of the advanced disease state of this patient population and the screening involved in defining eligibility. This event should be approved by the sponsor following discussions with the investigators.

All patients who enter Phase 2 will be assigned to nivolumab/galunisertib combination therapy by IWRS.

6. A Priori Statistical Methods

6.1. General Considerations

Statistical analysis of this study will be the responsibility of Lilly.

The interpretation of the study results will be the responsibility of the investigator with the Lilly CRP, pharmacokineticist, and statistician. The CRP and statistician will also be responsible for the appropriate conduct of an internal review for both the final study report and any study-related material to be authorized by Lilly for publication.

Additional exploratory analyses of the data not described in this plan will be conducted as deemed appropriate.

By default, listings will include the study part (Phase 1b/2), the dose cohort for Phase 1b and the histology cohort for Phase 2. Summaries will generally be split by part and cohort as well.

For continuous measures, summary statistics will include sample size, means, standard deviations and/or standard error, medians, minimums, and maximums. For categorical measures, summary statistics will include frequency counts and percentages. Any missing longitudinal data will not be imputed; rather statistics will be estimated from an appropriate mixed effects model, unless otherwise specified. Transformations will be applied where assumptions behind any analysis are better satisfied by data being transformed onto an alternative scale. All results from any of these analyses will be back transformed to the original scale. Alternatively, nonparametric methods will be applied.

All confidence intervals for clinical parameters that are estimated will have a nominal confidence grade of 95%, unless otherwise stated.

Statistical tests of treatment effects will be performed at a 2-sided significance level of 0.05, unless otherwise stated.

The following terms and data handling conventions (Table JBEF.6.1) will be used in the analysis.

Term	Definitions or Rule
Study day	If assessment is on or after date of first study drug dose then (date of assessment) – (date of first study treatment dose) $+ 1$.
	If assessment precedes first treatment dose then (date of assessment) – (date of first study treatment dose).
	There is no study day 0. Study day 1 is the date of first dose and study day -1 is the day before the first dose.
Cycle day	If assessment is on or after date of first study drug dose then (date of assessment) – (date of first study treatment dose in cycle) + 1.
	If SOE planned pre-dose assessment precedes first treatment dose date in that cycle then (date of assessment) – (date of first study treatment dose in cycle).
	There is no cycle day 0. Cycle day 1 is the date of first dose in the cycle and cycle day -1 is the day before the first dose.
Baseline	For change from baseline analysis, baseline value is defined as the last reported measure on or before the first dose date (or discontinuation, if no treatment is given). For change from baseline within a cycle, the measure prior to the first dose of that cycle is baseline.
Study treatment period	Time from treatment start to discontinuation from combination treatment or if the patient has previously discontinued from 1 of the 2 study drugs, ends on the date the decision to discontinue the patient from the remaining study drug.
Post-discontinuation – short-term follow-up (or safety follow-up)	Safety Follow-Up begins the day after the patient and the investigator agree that the patient will no longer continue combination treatment and includes 30-day and 100-day visits.
	 30-Day Follow-Up begins the day after the patient and the investigator agree that the patient will no longer continue study treatment and lasts approximately 30 days.
	 100-Day Follow-Up begins the day after the 30-day follow-up visit and lasts approximately 70 days or approximately 100 days after the patient is no longer receiving study treatment.
Post-discontinuation – long-term follow-up	Long-Term Follow-Up begins the day after 100-day follow-up is completed and continues until the patient's death or end of trial (the patient will be contacted approximately every 12 weeks \pm 7 days).

 Table JBEF.6.1.
 Terms and Data Handling Conventions

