6.2.4. Definitions of Study Periods

Terms used to describe the periods during the study are defined below:

- **Baseline or screening (= patient entering the study):** begins when the ICF is signed and ends at the first study treatment (or at discontinuation, if no treatment is given).
- **Study Treatment Period:** begins at the first study treatment (= **patient is enrolled in the study**) and ends on the date the decision to discontinue the patient from combination treatment or if the patient has previously discontinued from 1 or the 2 study drug, ends on the date the decision to discontinue the patient from remaining study drug.
- **Safety Follow-Up:** begins the day after the patient and the investigator agree that the patient will no longer continue combination treatment and includes 30-day and 100-day visits.
 - **30-Day Follow-Up** begins the day after the patient and the investigator agree that the patient will no longer continue study treatment and lasts approximately 30 days.

- **100-Day Follow-Up** begins the day after the 30-day follow-up visit and lasts approximately 70 days or approximately 100 days after the patient is no longer receiving study treatment.
- **Long-Term Follow-Up** begins the day after 100-day follow-up is completed and continues until the patient's death or end of trial (approximately every 12 weeks \pm 7 days the patient will be contacted).
- **Study Completion:** occurs (that is, the scientific evaluation will be complete) following the final analysis/evaluation of OS.
- **End of Trial:** The term "end of trial" refers to the date of the last visit or last scheduled procedure for the last patient (includes follow-up periods). The end of trial occurs after study completion, and after the last patient has discontinued study treatment and completed the 100-day follow-up (if applicable).

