8.4. Procedure/Sampling Compliance

Every attempt will be made to enrol patients who have the ability to understand and comply with instructions. Noncompliant patients may be discontinued from the study.

The collection times of safety assessments, PK samples, pharmacodynamic samples, and efficacy measurements are given as targets, to be achieved within reasonable limits. The scheduled time points may be subject to minor alterations; however, the actual collection time must be correctly recorded on the eCRF.

The scheduled collection times may be modified by the sponsor based on analysis of the safety and PK information obtained during the study. Any major modifications that might affect the conduct of the study, patient safety, and/or data integrity will be detailed in a protocol amendment.

9. Data Management Methods

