10.6. Biomarker Analyses

For details on biomarkers, see Section 8.2.3.

Pharmacodynamic data from all patients undergoing pharmacodynamic assessments will be analysed with appropriate standard nonlinear analytic software. Pharmacodynamic effects will be assessed by summary statistics, and investigated graphically to explore patterns of change over time, and how the patterns differ among dose levels or exposure. If there is a meaningful indication in the pattern over time, further analysis (eg, by linear mixed model) may be performed to characterise the relationship.

To identify and assess biomarkers for potential tailoring purpose, associations between baseline biomarker measures and clinical outcomes will be analysed using appropriate single-marker or multi-marker analysis approaches.

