Attachment 3. Protocol JBEF Hepatic Monitoring Tests for Treatment-Emergent Abnormality

Selected tests may be obtained in the event of a treatment-emergent hepatic abnormality and may be required in follow-up with patients in consultation with the Lilly CRP.

Hepatic Monitoring Tests

Hepatic haematology^a	Haptoglobin^a
Haemoglobin	
Haematocrit	Hepatic coagulation^a
RBC	Prothrombin time
WBC	Prothrombin time, INR
Neutrophils, segmented	
Lymphocytes	Hepatic serologies^{a,b}
Monocytes	Hepatitis A antibody, total
Eosinophils	Hepatitis A antibody, IgM
Basophils	Hepatitis B surface antigen
Platelets	Hepatitis B surface antibody
	Hepatitis B Core antibody
Hepatic chemistry^a	Hepatitis C antibody
Total bilirubin	Hepatitis E antibody, IgG
Direct bilirubin	Hepatitis E antibody, IgM
Alkaline phosphatase	
ALT	Antinuclear antibody^a
AST	
GGT	Anti-smooth muscle antibody^a
CPK	

Abbreviations: ALT = alanine aminotransferase; AST = aspartate aminotransferase; CPK = creatine phosphokinase; GGT = gamma glutamyl transferase; Ig = immunoglobulin; INR = international normalised ratio; RBC = red blood cells; WBC = white blood cells.

^a Assayed by Lilly-designated and local laboratory.

^b Reflex/confirmation dependent on regulatory requirements and/or testing availability.

Blood Biomarker Sampling Schedule

Pharmacodynamic Sample #	Cycle	Day	Sampling Windows for Blood Collection
1	1	1	Predose
2	1	1	2 hours postdose \pm 10 minutes
3	1	2	Predose
4	1	8	Predose
5	1	15	Predose
6	2	1	Predose
7	2	15	Predose
8	4	1	Predose
9	Follow-Up		

Abbreviation: V = visit.

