6.8.2. Pharmacodynamics and Tailoring Analyses

Biomarker data from all patients undergoing biomarker assessments will be analyzed using descriptive statistics. Biomarkers will be explored at baseline for prognostic value in efficacy or safety outcomes.

Further exploratory analyses of pharmacodynamic markers will be conducted as warranted.

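### The SAP fixes study baseline by calendar date, so a blood biomarker reported 2 hours after the first dose becomes its own baseline, which conflicts with Protocol 6.2.4

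*SAP*

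**What the plan says.** SAP section 6.1, Table JBEF.6.1, gives the data-handling conventions for the analysis. Its Baseline entry contains two rules.

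- For change from study baseline, the "baseline value is defined as the last reported measure on or before the first dose date". The only addition covers patients who discontinue untreated. There is no predose or clock-time condition.
- A separate sentence reads: "For change from baseline within a cycle, the measure prior to the first dose of that cycle is baseline".

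The same table works in whole days: "Study day 1 is the date of first dose". A predose and a postdose sample taken on that date therefore share one study day.

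Protocol 6.2.4 defines the baseline or screening period as one that "begins when the ICF is signed and ends at the first study treatment". In the Blood Biomarker Sampling Schedule (Protocol Attachment 4), sample 1 is Cycle 1 Day 1 predose and sample 2 is Cycle 1 Day 1, "2 hours postdose", with a 10-minute window either side.

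On use of the data, Protocol 10.6 says pharmacodynamic effects will be summarised and "investigated graphically to explore patterns of change over time". SAP 6.8.2 says "Biomarkers will be explored at baseline for prognostic value in efficacy or safety outcomes". Neither section sets a biomarker baseline of its own.

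**The concern.** A baseline should be the last value not yet influenced by treatment. The SAP's first rule drops that condition by replacing the moment of first treatment with its calendar date. For most measures the difference is harmless, because nothing is collected after the dose on that day. Blood biomarkers are the exception in the visible schedules: a sample is planned 2 hours after the first dose, and any early pharmacodynamic effect would show there.

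Followed as written, the rule would hide that early effect and carry it, with reversed sign, into every later change from study baseline. If the baseline-biomarker analyses of SAP 6.8.2 reuse the definition, a post-treatment value would also be tested as a prognostic factor. The graphs in Protocol 10.6 would be affected only if drawn as change from study baseline; plots of raw values need no baseline.

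**Working it through.** The plan states no figure on this point, so there is none to reproduce. The check applies the rule to the schedule.

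**Inputs**

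- Study-baseline rule and within-cycle rule: SAP Table JBEF.6.1.
- Nine blood biomarker samples, S1 to S9: Protocol Attachment 4.
- First dose of both drugs on Cycle 1 Day 1: Protocol Attachment 1.

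**Step 1: which sample is selected**

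| Rule | Cycle 1 Day 1 samples that qualify | Baseline |
|---|---|---|
| SAP rule: latest with date ≤ first dose date | S1 (predose), S2 (2 hours) | S2 |
| Date-time rule: latest with date and time < first dose | S1 | S1 |
| SAP within-cycle rule, Cycle 1 | S1 | S1 |

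The first two rows were run with S2 at the nominal time and at 10 minutes either side, with the same result each time. If S2 is not reported, the SAP rule and the date-time rule both give S1. So for an analyte reported at 2 hours, one SAP table cell yields two Cycle 1 baselines: S2 for change from study baseline and S1 for change within the cycle.

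**Step 2: effect on change from study baseline**

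With S2 as baseline, the change at sample k is

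S_k − S2 = (S_k − S1) − (S2 − S1).

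- For k = 2 this is S2 − S2 = 0 in every patient with a reported 2-hour value.
- For k = 3 to 9 it is the change from predose, shifted by −(S2 − S1).
- On the ratio scale, S_k/S2 = (S_k/S1)/(S2/S1), so the predose ratio is divided by the 2-hour ratio.

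If S2 = S1 there is no distortion.

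**Step 3: how many samples are affected** (analyte assayed at all nine times)

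After S1 there are 8 samples: S2 to S5 in Cycle 1 (2 hours, Day 2, Day 8, Day 15), which is 4, and S6 to S9 (Cycle 2 Day 1, Cycle 2 Day 15, Cycle 4 Day 1, follow-up), which is 4.

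| Situation | Fixed at 0 | Shifted | Affected |
|---|---|---|---|
| Study rule used throughout | 1 (S2) | 7 (S3 to S9) | 1 + 7 = 8 of 8 |
| Within-cycle rule governs Cycle 1, study rule afterwards | 0 | 4 (S6 to S9) | 4 of 8 |
| Analyte not assayed at 2 hours | 0 | 0 | 0 of 8 |

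These are counts of scheduled samples, not an effect size. The documents give no 2-hour effect, so S2 − S1, and with it the bias, cannot be put into numbers.

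**The case against.** The other side has five arguments.

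- **Protocol 6.2.4 defines a study period, not an analysis value.** The SAP cell also repeats its provision for untreated patients, so the authors probably meant to carry the predose idea over. This is likely, and it makes the wording a slip rather than a choice. The conflict stays: a value taken 2 hours after treatment lies outside the protocol's baseline period.
- **A 2-hour change is naturally a within-cycle change, for which the second rule gives the predose sample.** This stands in part, and it is why the lower count is 4 of 8. It does not repair the study-baseline rule, which still shifts the samples after Cycle 1, and the SAP does not say which rule governs a Cycle 1 biomarker change.
- **No named biomarker analysis is shown to use the rule.** It is worded for change-from-baseline analysis. SAP 6.8.2 plans descriptive statistics and prognostic exploration, and specifies no biomarker change endpoint. This stands and limits the reach.
- **Relevant material is not available.** The documents do not say which analytes are assayed at 2 hours, and SAP 6.8.1 refers to a separate PK/PD analysis plan that may set its own baseline. This also stands.
- **A date-time rule needs dose times as well as collection times.** That is correct. Protocol 8.2.2.1 has the patient diary record the time of every galunisertib dose in the first two cycles. A fallback to samples labelled predose covers a missing time.

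A programmer might well pick the predose sample regardless. A prespecified rule should not depend on someone departing from its text.

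**Conclusion.** The concern holds. Applied literally, SAP Table JBEF.6.1 takes a treated value as study baseline for any blood biomarker with a reported 2-hour sample on Cycle 1 Day 1, and nothing in the available text overrides it. This is a stated rule that gives the wrong value, not a missing detail.

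The textual error is certain; its consequence is conditional. Results are distorted only if all of these hold:

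- the analyte is assayed at 2 hours and has moved by then;
- it is analysed as change from study baseline, or its baseline is taken from this definition;
- no other plan sets a different baseline.

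Under those conditions, 8 of 8 later samples are affected, or 4 of 8 if the within-cycle rule governs Cycle 1. The biomarker objective is exploratory, and no primary or secondary endpoint is shown to be affected. The point merits correction but does not threaten the main conclusions.

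**What to change.** In SAP Table JBEF.6.1, define baseline as the last non-missing measure before the date and time of the first dose of either study drug. Where the time is missing on Day 1, use only samples labelled predose.

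For blood biomarkers, state three things:

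- Baseline is Cycle 1 Day 1 sample 1. If it is missing, use an earlier pretreatment sample where one exists. Protocol Attachment 1 marks a biomarker sample in the 14 days before Cycle 1 Day 1, but the Attachment 4 list starts at the Cycle 1 Day 1 predose sample, so a separate screening draw is not certain.
- The within-cycle rule gives the same baseline in Cycle 1.
- The baseline-biomarker prognostic analyses use this predose value.

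The cost is one table-cell edit and the matching line in the dataset specification. No new data are needed: Protocol 8.4 already requires that "the actual collection time must be correctly recorded on the eCRF", and the diary supplies galunisertib dose times. If the separate PK/PD plan defines its own baseline, the two should be aligned.

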6.1.1. Analysis Populations

All safety and efficacy analyses will be conducted on the safety analysis set (ie, patients who received at 1 dose of either galunisertib or nivolumab).

All patients who have received at least 1 dose of either galunisertib or nivolumab and have evaluable PK samples will be included in the analysis of PK.

Pharmacodynamics (PD) and/or tailoring biomarker analyses will be based on the subset of patients from the above populations from whom a valid assay result (according to laboratory guidelines) has been obtained.

6.1.2. End of Study Definitions

Per protocol, the following definitions apply:

- **Study Completion** corresponds to the final analysis/evaluation of OS. The final evaluation may occur before all patients reach the OS endpoint if this earlier evaluation will not alter the statistical interpretation of OS. Investigators will continue to follow the study schedule for all patients until notified otherwise by Lilly.
- The term "end of trial" refers to the date of the last visit or last scheduled procedure for the last patient (includes follow-up periods). The end of trial occurs after study completion, and after the last patient has discontinued study treatment and completed the 100-day follow-up (if applicable).

6.2. Adjustments for Covariates

Additional exploratory analyses may be performed on safety or efficacy measures to adjust for factors that may affect outcomes.

6.3. Handling of Dropouts or Missing Data

Rules for handling dropouts or missing data are listed by type of analysis. Unless otherwise specified, observed data will be used and missing data will not be imputed or carried forward.

General rules for imputing dates related to adverse event (AE) or concomitant therapy (pre-dose):

- Onset date of an AE or start date of a concomitant therapy:
 - If only the day is missing, the date will be set to:
 - First day of the month that the event occurred, if the onset yyyy-mm is after the yyyy-mm of first study treatment.
 - The day of the first study treatment, if the onset yyyy-mm is the same as yyyy-mm of the first study treatment.
 - If both the day and month are missing, the complete date will be set to:
 - January 1 of the year of onset, if the onset year is after the year of the first study treatment.
 - The date of the first dose, if the onset year is the same as the year of the first study treatment.
- Resolution date of an AE or end date of a concomitant therapy:
 - If only the day is missing, the date will be set to the last day of the month of the occurrence, or to the date of death if the patient died in the same month.
 - If both the day and month are missing, the date will be set to 31 December of the year of occurrence.

If a date is completely missing, then the AE will be considered treatment emergent. In case of additional therapies, the therapy will be considered concomitant.

General rule for imputing other dates: If a date variable is needed for an analysis, use the following general rule to impute incomplete date:

- If the date has no missing year and month but the day is missing, then assign 1 to the day
- If the date has no missing year, but has missing month, then assign January to the month.

However, after imputation, check if the imputed date is logically consistent with other relevant date variable(s) and make appropriate correction if necessary. For example, if a visit start date was 10 May 2015 and a tumour assessment date was xx May 2015 (missing day) but it was known that it occurred after that visit, then after imputation, the tumour assessment date became 01 May 2015. In this case, the imputed tumour assessment date should be compared to the visit start date and then corrected to be the visit start date, 10 May 2015.

Safety analysis: The following rule for missing data processing will apply for safety analysis:

- Missing classifications concerning study medication relationship will be considered as related to study medication (both components).
- If the AE onset date is missing or partial, the date will be compared as far as possible with the date of first dose of study medication when determining whether or not the AE is present at baseline. In this case, the AE will be assumed to be treatment emergent, unless there is clear evidence (through comparison of partial dates) to suggest that the AE started prior to the first dose of study medication.

Time-to-event analysis: All censored data will be accounted for using appropriate statistical methods as described in the efficacy section.

